9.2.4. Treatment Given as a Result of the Event

The event impact in terms of treatment provided will be as either: none, medication administered, non-drug therapy administered, surgery performed, hospitalization, or other (with a specification).

9.2.5. Event Outcome Assessment

The outcome of the event will be assessed as either: fatal, not recovered/not resolved, recovered/resolved, recovered/resolved with sequelae, recovering/resolving, or unknown. Only one AE per subject is allowed to have an outcome assessment as "death." If there are multiple causes of death for a given subject, only the primary cause of death will have an outcome of death.

9.3. SERIOUS ADVERSE EVENT (SAE) DEFINITION

A SAE is defined as any AE that:

- Results in death
- Is life threatening (the subject is at immediate risk of dying from the adverse experience)
- Requires subject hospitalization or prolongs existing hospitalization
- Results in persistent or significant disability/incapacity
- Is a congenital anomaly/birth defect
- Important medical events that may not result in death, be life-threatening, or require hospitalization may be considered a serious adverse effect when, based upon appropriate medical judgment, they may jeopardize the subject or subject and may require medical or surgical intervention to prevent one of the outcomes listed in this definition.

9.4. REPORTING OF SERIOUS ADVERSE EVENTS (SAEs)

The Investigator is required to report all SAEs that occur during the time period specified in [Section 9.2](#). Once the Investigator becomes aware of an SAE, he/she must report the SAE to Medical Monitor within 24 hours.

Attn: Amarex Clinical Research, LLC
[name]
[name]

The Medical Monitor may request additional supporting documentation as it becomes available, such as lab reports, electrocardiogram [ECG] reports, discharge summary, hospital notes, etc., if applicable. Additional follow-up information as it becomes available must be reported to the Medical Monitor.

The Investigator is also responsible for reporting all SAEs to the appropriate Institutional Review Board (IRB) in accordance with local laws and regulations. The Investigator is responsible for maintaining documentation in the study file that indicates the IRB has been properly notified.

9.4.1. SAE Follow-Up

All subjects experiencing an SAE, including the discontinued subjects, must be closely followed until sufficient information is obtained to indicate a return to normal status or until the event stabilizes at a level acceptable to the investigator or the last study visit, whichever occurs first (i.e., recovery, return to baseline status, no further improvement expected, or death).

For each SAE indicated as an unresolved event on the initial report, regardless of whether the subject completed the study or withdrew, the site should submit a follow-up report with updated information.

9.5. PREGNANCY REPORTING

To ensure patient safety, any pregnancy that occurs while subject is taking study drug, any pregnancy that occurs in a female subject or a female partner of a male subject from the time of first study treatment administration till 30 days after the last treatment administration should be recorded using a Pregnancy Notification Report Form and reported immediately to Sponsor within 24 hours of learning of the pregnancy.

If a female subject becomes pregnant during the study before the end of treatment period, they will be a discontinued subject. If a subject becomes pregnant during the study after the end of treatment during the follow up portion, they can complete the remaining scheduled follow up visits unless there is a medical contraindication.

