1.5.1. Pregnancy

Any pregnancy that occurs while taking study drug should be recorded using a Pregnancy Report Form and reported immediately to Sponsor within 24 hours of learning of the pregnancy. See [Section 9.5](#) for more information on reporting of pregnancy.

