 14. Negative pregnancy test for female subjects of childbearing potential. Women of childbearing potential (WOCBP) and Women of non-childbearing potential are eligible to participate. Both women of childbearing potential and women of non-childbearing potential should use an approved method of birth control and agree to continue to use this method for the duration of the study (and for 90 days after taking the last dose of study drug).

Acceptable methods of contraception include abstinence, female subject/partner's use of hormonal contraceptive (oral, implanted, or injected) in conjunction with a barrier method (WOCBP only) (e.g., diaphragm, cervical cap, male condom, and female condom and

spermicidal foam, sponges, and film), female subject/partner's use of an intrauterine device (IUD), or if the female subject/partner is surgically sterile for at least three months before screening or 2 years post-menopausal at time of screening. All male subjects/partners must agree to consistently and correctly use a condom for the duration of the study and for 90 days after taking the study drug. In addition, subjects may not donate sperm for the duration of the study and for 90 days after taking study drug.

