9.2. REPORTING OF ADVERSE EVENTS (AEs)

Report initiation for all AEs and SAEs will begin at the time of the first treatment visit and continue until the end of final study visit. All events will be followed to resolution or until the subject completes the study. A final assessment of outcome will be made at that time.

All AEs must be recorded in the subject's medical records and on the CRF. AEs will be reported using customary medical terminology along with the following information: the onset and end dates, whether the event is considered to be a SAE (see [Section 9.3](#)), the impact the event had on study treatment (see [Section 9.2.1](#)), the Common Terminology Criteria for Adverse Events (CTCAE) grade (intensity) of the event (see [Section 9.2.2](#)), the causality of the event (see [Section 9.2.3](#)), whether treatment was given as a result of the event (see [Section 9.2.4](#)), and the outcome of the event (see [Section 9.2.5](#)).

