9.5.1. AE and SAE Reporting

Pregnancy itself is not regarded as an AE unless there is a suspicion that the IP may have interfered with the effectiveness of a contraceptive medication. Pregnancy in a subject's partner is not considered an AE. Congenital abnormalities/birth defects and spontaneous miscarriages should be reported and handled as SAEs.

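### Required pregnancy notification ends 30 days after the last treatment although contraception is required for 90 days, so 60 of those 90 days carry no readable notification duty

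*Protocol*

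**What the plan says.** **Notification.** Protocol section 9.5 asks for a notification form and a report to the sponsor within 24 hours. It covers pregnancies in female subjects and in female partners of male subjects "from the time of first study treatment administration till 30 days after the last treatment administration". Its second paragraph foresees a subject becoming pregnant during follow-up, but addresses only whether she may complete her visits.

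**Contraception.** Inclusion criterion 14 (section 3.4.1, repeated in the synopsis) asks women to use contraception during the study and "for 90 days after taking the last dose of study drug". Male subjects and partners must "use a condom for the duration of the study and for 90 days after taking the study drug", and "subjects may not donate sperm for the duration of the study and for 90 days after taking study drug".

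**Summary wording.** Section 1.5.1 says "Any pregnancy that occurs while taking study drug should be recorded using a Pregnancy Report Form" and then refers the reader to 9.5.

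**Adverse event rules.** Under section 9.2, AE and SAE reporting starts at the first treatment visit and is to "continue until the end of final study visit". Section 9.5.1 adds: "Congenital abnormalities/birth defects and spontaneous miscarriages should be reported and handled as SAEs". It makes pregnancy itself an AE only if the product is suspected of interfering with a contraceptive medication, and it never counts a partner's pregnancy as an AE. Section 9.5.1.1 makes therapeutic abortion an SAE and leaves elective abortion without medical reason outside AE reporting.

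**Follow-up and outputs.** Section 4.4.2 provides contact at least every 3 months and 2 years of follow-up; the list of assessments is redacted. SAP sections 8.3.13 and 8.3.14 plan listings and/or summaries of pregnancy notifications and outcomes.

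**The concern.** The protocol asks subjects to take precautions for 90 days after study drug, yet the section that governs pregnancy notification stops at day 30. A site following 9.5 exactly would have no duty to notify a pregnancy that begins between those two dates. AE reporting runs longer but does not fully close the gap, because a pregnancy is generally not an AE.

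At stake is the completeness of a safety record. Without notification there is no trigger for the 24-hour report, and the follow-up to outcome in 9.5.3 starts only from a pregnancy the site knows about. Adverse outcomes that reach the database as SAEs would have no count of exposed pregnancies to be set against.

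**Working it through.** The documents derive no figure on this point, so there is nothing to reproduce. The check compares two windows and then looks for any other rule that covers the difference.

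**Inputs, in days after the last dose**
- Notification limit, r = 30 (section 9.5).
- Contraception period, c = 90 (criterion 14).

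**Step 1. Days not covered.** c − r = 90 − 30 = 60. Share = (c − r)/c = 60/90 = 66.7%. With the limits aligned at 90 it would be (90 − 90)/90 = 0%.

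**Step 2. Sensitivity to the reading of criterion 14.** Precautions are also required for the duration of the study. If that is taken literally to include the 2-year follow-up, and follow-up is assumed to last 730 days from the last dose, the share is (730 − 30)/730 = 700/730 = 95.9%. The 90-day reading gives the smaller gap and is the one used here.

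**Step 3. Other routes for a pregnancy beginning on days 31 to 90**

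| Event | Route in the readable text |
|---|---|
| Spontaneous miscarriage, birth defect | SAE (9.5.1), if before the final study visit (9.2) |
| Therapeutic abortion | SAE (9.5.1.1), same limit |
| Pregnancy with suspected interference with a contraceptive medication | AE (9.5.1) |
| Uncomplicated pregnancy in a subject | None found |
| Elective abortion without medical reason | None found |
| Partner pregnancy without an SAE outcome | None found; not an AE (9.5.1) |

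**Step 4. Starting point in Part 2.** Section 9.5 counts from the last treatment administration and criterion 14 from study drug; neither names a drug. In Part 2 two drugs are given, and section 4.4.1 counts the End of Treatment visit from the last dose of 2X-121. If the two drugs stop on different days, the text does not say which date starts either count.

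**The case against.** The case against has five parts.

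1. **Serious outcomes have a route.** SAE reporting lasts until the final study visit, and section 9.4 requires a report to the medical monitor within 24 hours. This stands. A reader might infer that pregnancies on days 31 to 90 are lost to safety follow-up altogether; the documents do not support that. The gap concerns notification of the pregnancy itself and, for the last three rows of the table, any required report at all.

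2. **Section 1.5.1 is not a third window.** It is a short summary that defers to 9.5, and 9.5 opens with the same on-treatment wording before extending it. This stands. The conflict is between two windows, and 1.5.1 only needs conforming.

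3. **Sections 9.5.2 and 9.5.3 have no 30-day limit.** The consent form covers information through the end of pregnancy, and pregnancies are followed to outcome. That is correct, and outcome follow-up on days 31 to 90 is not excluded. But neither section creates a duty to notify.

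4. **Redaction.** The follow-up assessments and the row labels of the schedules are blacked out, so questions about pregnancy there cannot be excluded. This stands as a limit on certainty. The readable rule still ends at day 30.

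5. **The windows need not match, and few cases are expected.** No readable text requires the two periods to be equal, and at most 16 + 24 = 40 subjects are planned. Both facts limit the importance of the point. Neither explains why a period of required precautions should go without required notification.

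**Conclusion.** The point holds in limited form. Sections 9.5 and 3.4.1 do not agree, and as written 60 of the 90 post-dose contraception days carry no readable duty to notify a pregnancy. The consequence falls on uncomplicated pregnancies, elective abortions and most partner pregnancies.

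The two thirds is a share of calendar days. A reader might take it as the share of pregnancies, or of reproductive risk, that is missed. The documents support neither: they give no pregnancy rate, no distribution of risk over the 90 days, and nothing to suggest that the on-treatment period is uncovered.

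The conclusion assumes that the redacted follow-up assessments contain no separate pregnancy rule, and that 90 days is the intended contraception period. It is a correction to safety-data capture that should be made. It does not bear on the MTD determination, the sample size or any planned comparison.

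**What to change.** - Reconcile section 9.5 with inclusion criterion 14 (section 3.4.1 and synopsis), so that notification and outcome follow-up, for female subjects and for female partners of male subjects, run at least as long as the contraception period. The length of that period is for the sponsor to confirm.
- Conform the summary sentence in section 1.5.1.
- State which drug's last dose starts the count in Part 2.
- Have sites ask about pregnancy at the 3-monthly follow-up contacts, unless the redacted assessments already include this. A pregnancy that begins late in the window may become known only at a later contact, so the question should not be confined to the first one.

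The cost is a sentence in each of 9.5 and 1.5.1 and one question at contacts that already take place. The consent provision in 9.5.2 already extends to the end of pregnancy, and the SAP outputs need no change.

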9.5.1. AE and SAE Reporting

Pregnancy itself is not regarded as an AE unless there is a suspicion that the IP may have interfered with the effectiveness of a contraceptive medication. Pregnancy in a subject's partner is not considered an AE. Congenital abnormalities/birth defects and spontaneous miscarriages should be reported and handled as SAEs.

9.5.1.1. Abortions

An induced elective abortion to terminate a pregnancy without medical reason is not regarded as an AE. However, an induced therapeutic abortion to terminate a pregnancy because of complications or medical reasons must be reported as an SAE. The underlying medical diagnosis for this procedure should be reported as the SAE term. A spontaneous abortion is always considered an SAE.

9.5.2. Informed Consent

The ICF will include information regarding reporting of pregnancy to the Sponsor and collection of information through the end of pregnancy that occurs in either a female subject or in a female partner of a male subject. If a female partner becomes pregnant, the Investigator will request consent from the partner to collect this information.

9.5.3. Pregnancy Follow-Up

The pregnancy will be followed-up to determine the outcome (spontaneous miscarriage, elective termination, ectopic pregnancy, normal birth, or congenital abnormality) and should include an assessment of the possible relationship to the study treatment of any pregnancy outcome. This information should also be documented on the Pregnancy Outcome Report Form and reported to the Sponsor.

10. DIRECT ACCESS TO SOURCE DATA/DOCUMENTATION

Subjects will be identified on CRFs by a unique subject identification number and on source documents by name and date of birth. No personal identifier will be used in any publication or communication used to support this research study. The subject identification number will be used if it becomes necessary to identify data specific to a single subject.

The local IRB, FDA, the monitors, auditors and personnel authorized by the Sponsor are eligible to review the medical and research records related to this study as part of their responsibility to protect human subjects in clinical research. They will be given direct access to source data and documentation (e.g., medical charts/records, printouts etc.) for source data verification, provided that subject confidentiality is maintained in accordance with local requirements. Access to electronic medical records may be governed by institution policy. Each site will be required to ensure access while remaining compliant with institutional requirements.

11. QUALITY CONTROL AND QUALITY ASSURANCE

11.1. MONITORING REQUIREMENTS

The specific obligations outlined in 21 Code of Federal Regulations (CFR) and ICH guidelines require the Sponsor to maintain current personal knowledge of the progress of a study. Therefore, the Sponsor's designated monitor will visit the site during the study as well as maintain frequent telephone and written communication. The Investigator will permit the Sponsor to monitor the study as frequently as is deemed necessary and provide access to medical records to ensure that data are being recorded adequately, that data are verifiable and that protocol adherence is satisfactory.

As delineated above, the Investigator will permit representatives of the Sponsor and/or designated CRO to inspect all CRFs and corresponding study subject original medical records (source documents) at regular intervals throughout the study. Subject original medical records and other relevant data must be available to support all data recorded in the CRF. In addition to the original medical records, these data may include but are not limited to study, laboratory reports, etc.

In accordance with federal regulations, site inspections will serve to verify strict adherence to the protocol and the accuracy of the data that is being entered on the case report forms. A Monitoring Log will be maintained at each study site. The Monitoring Log will be signed by the monitor, dated and stated the type of visit. The Investigator should be aware that the study site and subject records may be inspected by the Sponsor and or representatives of the designated CRO, FDA or other regional regulatory authority.

11.2. ACCEPTABILITY OF CASE REPORT FORMS (CRFs)

For each subject who has signed an informed consent form, a CRF must be completed. For subjects who are screen failures, this would be limited to the screen failure CRF page. All source documents and CRFs will be completed as soon as possible after the subject's visit and corrections to data on the CRFs will be documented, if applicable. The Investigator will review the CRFs to indicate that, to his/her knowledge, they are complete and accurate. CRFs will be reviewed by the Sponsor's or designated CRO's monitor, who will make a decision as to their acceptability.

11.3. MODIFICATION OF PROTOCOL

The Investigator will not modify or alter this protocol without first obtaining the concurrence of the Sponsor. Approval by the Investigator's IRB must also be obtained prior to implementation of the change, with two exceptions:

1. When necessary to eliminate apparent immediate hazard to the subject; or
2. When the modification does not involve the subject's participation in the trial.

An amendment may also require modification of the informed consent form. The Investigator will provide an approval letter for the amendment and revised informed consent form, if applicable, to the Sponsor. An amendment must be provided in writing and it must be dated by both the Sponsor and the Investigator. If necessary, the Sponsor will submit protocol amendments to FDA and other appropriate regulatory authorities and notify other Investigators using this protocol.

11.4. REPORTING PROTOCOL DEVIATIONS

The Investigator is obligated to follow the protocol without departure from the requirements written in the protocol. If the Investigator deviates from the protocol requirements, the Sponsor will make the determination as to whether the subject will continue in the study. The Sponsor also has the right to discontinue the subject for protocol violations. The IRB may also have to be contacted if safety to the subject or if the scientific soundness of the study is involved. All protocol deviations must be documented in the CRFs.

11.4.1. Major Protocol Deviation or Violation

A major protocol deviation or violation is a deviation from the IRB approved protocol that may affect the subject's rights, safety, or well-being and/or the completeness, accuracy, and reliability of the study data. Examples of this include:

- Failure to obtain informed consent prior to initiation of study-related procedures
- A research subject does not meet the protocol's eligibility criteria but was enrolled without prior approval from the sponsor.
- A research subject received the wrong treatment or incorrect dose.
- A research subject met withdrawal criteria during the study but was not withdrawn.
- A research subject received a prohibited concomitant medication.
- Failure to treat research subjects per protocol procedures that specifically relate to primary efficacy outcomes.
- Changing the protocol without prior sponsor and IRB approval.
- Multiple minor violations of the same nature after multiple warnings.

11.4.2. Minor Protocol Deviation or Violation

A minor protocol deviation is any change, divergence, or departure from the study design or procedures of a research protocol that has not been approved by the IRB and which DOES NOT have a major impact on the subject's rights, safety or well-being, or the completeness, accuracy and reliability of the study data. Examples of this include:

- Follow-up visits that occurred outside the protocol required time frame because of the participant's schedule.

- Blood samples obtained at times close to but not precisely at the time points specified in the protocol.

12. INDEPENDENT DATA MONITORING COMMITTEE (IDMC)

Not applicable.

13. ETHICS AND REGULATORY REQUIREMENTS

This study is to be conducted in accordance with the specifications of this protocol and in accordance with principles consistent with Declaration of Helsinki, GCP, 21 CFR, ICH E6, HIPAA regulations in 45 CFR Part 164 (US only), and the Belmont Principles of respect for persons, beneficence, and justice. No protocol changes will be implemented without the prior review and approval of the IRB, except when the modification does not involve the subject's participation in the trial or where it may be necessary to eliminate an immediate hazard to a research subject. In the latter case, the change will be reported to the IRB as soon as possible, according to IRB regulations.

Additionally, the study product used in this study is manufactured, handled and stored in accordance with applicable GMP. The study product provided for this study will be used only in accordance with this protocol.

13.1. INSTITUTIONAL REVIEW BOARD/INDEPENDENT ETHICS COMMITTEE (IRB/IEC)

The Principal Investigator (PI) at each site will provide the Institutional Review Board/Independent Ethics Committee (IRB/IEC) with all appropriate materials as required by their IRB/IEC, including but not limited to the clinical study protocol, informed consent form, and any advertising materials. The study will not be initiated until the IRB/IEC provides written approval of the aforementioned documents and until approval documents have been obtained by the Principal Investigator and Sponsor or Sponsor designee. The Investigator will not participate in the decision. If the Investigator is an IRB or IEC member, documentation must be provided indicating recusal from the approval process. Appropriate reports on the progress of this study by the Principal Investigator will be made to the IRB/IEC as required by local and applicable government regulations and in agreement with policy established by the Sponsor. The Investigator is required to maintain an accurate and complete record of all written correspondence to and received from the IRB/IEC and must agree to share all such documents and reports with the Sponsor.

No changes from the final approved protocol will be initiated without the IRB/IEC's prior written approval or favorable opinion of a written amendment, except when necessary to eliminate immediate hazards to the subjects or when the modification does not involve the subject's participation in the trial.

